As per guidance from previous REC feedback, the below protocol has been briefly piloted and reviewed with two adolescent experts by experience (EBEs). In a series of meeting, we tested several components of the following design and we proceeded with minor amendments based on their feedback. Their feedback was used to inform the below study protocol.

Phase 0-A: Screening.

The participating NHS clinics will identify and screen potential participants using the inclusion criteria. The partnering NHS clinics will provide some information about the aims and objectives of the study to adolescents and their parents/ carers. The participants will be given a flyer containing the QR code link to Qualtrics, to begin the onboarding process.

Phase 0-B: Enrolment.

Using a QR link to a Qualtrics survey, participants (and their caregiver, if they are aged 12-16) will view the study information sheet and proceed to the consent/assent form, should they wish to participate. Consent will be obtained electronically via Qualtrics. Participants will receive a copy of the information sheet and completed consent/assent form via email. Upon gaining consent, we will contact participants to begin Phase 1.

Phase 1: pre-baseline.

Participants will spend a total of 1-2 weeks completing an online questionnaire (Process Based Assessment Tool; PBAT). Participants will receive completion prompts via the mPath app, on 3-4 days per week, and the questionnaire will take up to 3-4 minutes to complete. The PBAT questionnaire will collect data to track how adolescents cope with their headaches. This information will help the research team to develop the personalised plan for the psychological intervention in Phase 4 (described further on).

Phase 2: Personalisation and case conceptualization.

HeadFlex study

Project proposal, Royal Holloway University of London V3

Version and date: V3, September 2024

IRAS project number: 340890

PI: [name], C.Psychol (Clinical & Health) Royal Holloway, University of London

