We will meet with each adolescent online for 1 hour to collect further information using an intake assessment form (see the attached "Intake assessment form"). The form will assess headache history and coping responses. The research team will combine the information gathered in phase 1 and phase 2 to create a case conceptualisation. We will also create some brief goals for treatment and will identify key target processes (e.g., psychological coping responses, such as learning what to do during a headache episode) for the personalised intervention. We will collaboratively select 2-3 most personally relevant items from the previously completed PBAT questionnaire (in phase 1), which will form part of further data collection. These questionnaire items will be those deemed to be most relevant to the adolescents' presenting headache concerns, and these will guide the focus of the upcoming intervention. Finally, in Phase 2 we will introduce the upcoming data collection schedule which is described in Phase 3 below.

Phase 3: baseline data.

Participants will begin the Ecological Momentary Assessment (EMA), which they will complete 2-3 times per day, on 3- 4 days per week. The participants will be sent completion prompts via the mPath app. The questionnaires will take up to 2 minutes to complete each time. As per feedback from experts by experience, data collection will be distributed over several days per week to reduce participant burden (e.g., Monday, Wednesday and Friday). At this stage, participants will be completing both primary outcome measures (headache activity, progress towards the personalised goal, and coping with headache), and their personalised PBAT items. Once per week, participants will also receive a questionnaire assessing headache interference and headache-related disability.

Phase 4: intervention and further data gathering.

Each participant will be invited to attend up to 5 weekly online brief therapy sessions, lasting 30 minutes each, to work on the specific target processes identified in Phase 2. The personalised interventions will be drawn from already known evidence-based CBT-based treatments for headache

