Data collection schedule: In line with recommendations arising from 24 EMA studies with adolescents, a “burst design” for data collection may be optimal to reduce participant burden (Heron et al, 2017). Participants will therefore have periods of breaks from data collection during each week. This has also been advised by EBEs who took part in trialling the data collection schedule. Compliance with questionnaire completion will also be measured.

Phase 5: Follow-up.

Following intervention completion, participants will continue completing daily questionnaires for a further 1-2 weeks, as well as weekly measures of headache-related disability and interference.

Study end. At the end of the follow-up period, participants will be contacted by email to inform them of the end of the study and to thank them for their participation. Additionally, we will offer an optional online debrief meeting to each participant.

Sample recruitment

The sample will be recruited from a specialist paediatric NHS service (initial discussions are currently ongoing). Clinical staff will identify participants by screening adolescents against the criteria and seeking verbal consent to pass their details to the research team to discuss study participation.

We aim to recruit an adolescent sample size of 12 (to allow for sample attrition) ranging in ages 12-18. We are aiming for a final sample of $n=6$ (i.e. number of participants who complete the study). This sample size is in line with other previous SCED studies with adolescents (e.g., Cawthorne et al., 2022; Sukhodolsky et al., 2013).

Table 1.

Inclusion and exclusion criteria for the study:

Inclusion	Exclusion

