
 - Adolescents aged 12-18. - Recurrent headaches occurring for 3 months or more, ideally (but not necessary)-diagnosed by a paediatric Neurologist (diagnosis of any idiopathic headache, using the International Classification of Headache Disorders criteria (ICHD-3 beta version). - The headache should be deemed to be resulting from a primary headache disorder as opposed to a secondary symptom of another health condition. - Currently not receiving psychological support elsewhere or have prior accengagement with psychological support for or due to headache for the past 6 months prior to screening. - Reporting PedMIDAS score of greater than 10 points (indicating at least minimal disability) - Adolescent and their caregiver fluent in speaking and writing in English - Frequent access to a smartphone and access to the internet whether public (e.g., library) or private (e.g., home, personal) 	
 - Presence, history or suspicion of secondary headache disorder- - PedMIDAS of greater than 140 points (indicating excessive disability and need for multisystemic therapies). - Adolescent and their carer not fluent in speaking and writing in English. - Diagnosis of pervasive developmental disorder or serious mental condition (eg, psychosis, active suicide thoughts) as determined by the referral (either the parent/carer or the medical professional) - Adolescents living in families in distress (e.g., a family member experiencing another illness, mental health problem or psychosocial issues) - Limited access to a smartphone device with consistent internet connection. - Receiving psychological support elsewhere or have a prior engagement with psychological support for headaches up to 6 months prior to screening.

Assessment procedures

Demographics and clinical characteristics

HeadFlex study

Project proposal, Royal Holloway University of London V3

Version and date: V3, September 2024

IRAS project number: 340890

PI: [name], C.Psychol (Clinical & Health) Royal Holloway, University of London

Demographic information will be collected using Qualtrics between Phase 1 and 2. This will include the adolescent's age, gender, cultural background, headache diagnosis, headache profile (e.g., frequency, intensity, severity), and medication use.

Measures

Primary outcome measures

The primary outcome measures will be a series of Visual Analogue Scale (0-100) items that measure the following:

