To address the second research question, we will examine change in personalised goal, headache activity (VAS items), and personalised processes of change (BPAT) across time. The longitudinal data will be plotted on a line graph to allow a visual analysis for patterns, trends and variability in the data (Dowdy et al., 2022). We will supplement the visual analyses with Tau-U statistical analyses to assess the proportion of overlap between phases.

We will additionally follow a tutorial by McDonald (2022) to conduct individual dynamic regression analyses using a time-lag model, using SPSS. We will develop models, based on periods of feedback provision (one per week- overall 5 tested models). For these analyses we will estimate the

autocorrelations with lag numbers representing previous data points (e.g., data from sessions 1-5 will be included). The lagged idiographic outcome variables (headache interference and activity) will be entered into the regression model along with predictor(s) (the BPAT items) to identify whether a significant relationship exists between the predictor and the outcome, while accounting for any autocorrelation.

Ethical considerations

This study will require ethical approval from the RHUL Ethics Committee and the NHS Research Ethics Committee. Research guidelines and principles of the BPS Code of Ethics and Conduct will be followed throughout the project. Several ethical issues arising from this research are detailed below:

Informed Consent

Informed consent will be sought from both the participant and their primary caregiver or parent. Consent will be obtained electronically and, and electronic signed copies of consent forms will be stored in a RHUL's databases, accessible only to the research team. Appropriate time will be given during enrolment to ensure that participants fully understand the purpose of the study and study requirements. Participants and their caregivers will be provided with an e-copy of the information sheet.

Participants and their caregivers will be made aware that their involvement with the study is fully voluntary and that they are able to withdraw from the study at any point without justification, which will not impact their reimbursement for participating. Participants will also be made aware that any data collected up until the point of withdrawal will be anonymised and retained for analysis, to protect the validity of the study.

HeadFlex study

Project proposal, Royal Holloway University of London V3

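### The exclusion for active suicidal thoughts rests on the referral, and no described step before EMA begins requires anyone to ask the adolescent

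*Protocol*

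**What the plan says.** The exclusion column of Table 1 lists a pervasive developmental disorder or a serious mental condition, with psychosis and active suicidal thoughts as examples of the latter, "as determined by the referral (either the parent/carer or the medical professional"). The adolescent is not named as a source.

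The steps before EMA are as follows.

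- **Sample recruitment:** "Clinical staff will identify participants by screening adolescents against the criteria", and they do so while "seeking verbal consent to pass their details to the research team to discuss study participation". Phase 0-A mentions only the inclusion criteria.
- **Phase 0-B:** electronic information and consent or assent, then "Upon gaining consent, we will contact participants to begin Phase 1". The Informed Consent section adds that "Appropriate time will be given during enrolment to ensure that participants fully understand the purpose of the study and study requirements".
- **Phase 1:** one to two weeks of the PBAT questionnaire. "Participants will receive completion prompts via the mPath app, on 3-4 days per week".
- **Phase 2:** "We will meet with each adolescent online for 1 hour to collect further information using an intake assessment form". "The form will assess headache history and coping responses".
- **Phase 3:** EMA begins.

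The Confidentiality and Risk sections then cover helpline details, GP awareness, contact with the team, and what is done when risk appears.

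**The concern.** Suicidal thoughts are an internal state. A parent or a headache clinician can report only what they have seen or been told. If the exclusion is applied exactly as Table 1 words it, an adolescent whose thoughts neither source knows about can be enrolled, although the sponsor means to exclude that person. Participants may be as young as 12.

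Two features of the protocol make the referrer's knowledge a thin basis; both are inferences from its text. Recruits should not be receiving psychological support elsewhere, so there should be no current therapist elsewhere who might know. Phase 0-B also brings the caregiver into enrolment only for ages 12 to 16, although the Informed Consent section speaks of consent from both, so the parental source may be weaker for the oldest participants.

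The Risk section itself gives completion of the EMA questionnaires as an example of how distress may arise. The useful time to ask is therefore before EMA starts.

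**Working it through.** The protocol gives no figure on this point to reproduce. The check is to take each described step before Phase 3 and see whether it requires asking the adolescent about suicidal thoughts.

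1. **Clinic screening (Phase 0-A, Sample recruitment).** Staff screen adolescents, but the method is not stated. Asking is possible but not required. The mental-condition exclusion has no counterpart in the inclusion column, which is the only column that Phase 0-A mentions.
2. **Enrolment (Phase 0-B, Informed Consent).** This is electronic, with time allowed so that participants understand the study. No risk question is described.
3. **Contact after consent.** Its stated purpose is to begin Phase 1. No content is given.
4. **Phase 1.** PBAT questionnaires only. The items are not reproduced, so they cannot be judged.
5. **Phase 2 intake.** This is the first described meeting with each adolescent. The form's stated content is headache history and coping. The form itself is an attachment that is not reproduced, so it may contain more.

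No described step requires the question.

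**Exposure before the first described meeting.** Inputs from Phase 1: 1 to 2 weeks, 3 to 4 prompted days per week, up to 3 to 4 minutes per questionnaire. Assumption: one questionnaire per prompted day.

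- Prompted days: 1 × 3 = 3 to 2 × 4 = 8.
- Questionnaire time: 3 × 3 = 9 minutes to 8 × 4 = 32 minutes.

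**Cost of asking.** Assumption: 1 to 2 minutes per person asked.

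- Phase 2 meeting, up to 12 recruits: 12 × 1 = 12 to 12 × 2 = 24 minutes in total.
- Clinic screening, if every screened adolescent is asked: N × 1 to N × 2 minutes, where N is the number screened. The protocol does not give N. It is at least 12 if 12 are recruited, so 12 to 24 minutes is a lower bound for this part.

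**Room for late exclusions.** The plan recruits 12 to finish with 6, which allows 12 − 6 = 6 losses. Each participant found ineligible at Phase 2 would use one of these.

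**The case against.** The strongest reply is that Table 1 states who makes the determination, not what evidence they may use. An adolescent who tells the screening clinician is already covered, because that disclosure counts through the medical professional. Clinical staff of a specialist paediatric service may ask as a matter of course, and the protocol need not script how they do so. This stands, and it narrows the gap to thoughts that the adolescent has told neither source.

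A reader might also infer that the plan does nothing until risk shows itself. The text does not support that. Helpline details are on the information sheet, which is viewed before consent; the GP is aware of participation; and the team can be contacted throughout. These safeguards do not depend on a disclosure. They are not an eligibility check, however, so they do not close the gap.

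A third point is that the exposure before any meeting is small, and that the one-hour Phase 2 meeting comes before the EMA that the Risk section names. This also stands. It argues for putting the question in that meeting rather than adding a live contact before Phase 1.

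Finally, the intake form and some of the protocol text are not available, so a risk question may exist there. The finding is limited to what the available text requires.

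**Conclusion.** The point holds in a limited form. The determination is fixed on the referral, it can miss suicidal thoughts disclosed to neither source, and no described step before EMA requires the adolescent to be asked. The line should be changed because it concerns the safety of minors and the change is cheap. It is a matter of eligibility, not of the analysis.

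Three stronger readings are not supported. The text does not say that an adolescent's own disclosure is ignored, or that nobody will ask; it only fails to require asking. The word linking the two sources most naturally means that a positive report from one of them excludes, not that one of them can clear the adolescent. Nor can the mention of inclusion criteria in Phase 0-A be read as leaving exclusions unscreened, since the recruitment section refers to the criteria generally.

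The size is an assumed 1 to 2 minutes per person asked, against 9 to 32 minutes of early questionnaires if one is sent per prompted day. The frequency of undisclosed thoughts is unknown here, and no probability of harm is claimed.

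**What to change.** Amend the Table 1 line so that, after "as determined by the referral (either the parent/carer or the medical professional") it continues: or by the adolescent's own report. Then add two short instructions.

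- The clinic's screening clinician asks the adolescent directly where possible. A positive answer at this stage comes before study consent, so it is handled under the clinic's own procedures.
- The research team asks once in the planned Phase 2 meeting, before EMA starts. A positive answer is handled under the pathway in the Confidentiality and Risk sections.

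No separate live contact before Phase 1 is needed.

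The cost is one amended line, 12 to 24 minutes in total across up to 12 Phase 2 meetings, and at least as much again at the clinic if everyone screened is asked, including those not recruited. Time to act on positive answers is extra. A participant may be found ineligible after giving Phase 1 data, so the protocol should say how such data are treated. The question will not find every case: the Risk section has caregivers told of significant risk, which may limit candour, so it is best asked in private.

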A distinct aspect of PBT intervention is ongoing data collection, using methods such as Ecological Momentary Assessment (EMA). Using EMA, we will repeatedly sample symptoms, coping with headache responses, and relevant pain-related behaviours. EMA collects data that captures frequent momentary information from adolescents in the context of their lives, longitudinally (Hedeker et al., 2012). It also helps adolescents increase self-awareness, insight, and self-management of their

headache difficulties (Folkersma et al. 2021). In this study, we will use EMA to collect weekly data, which will inform progress tracking and allow personalised treatment trajectory.

Aim of the project and research question

The objective of this project is to construct idiographic case conceptualisations and deliver brief personalised interventions, guided by weekly data that will inform the course of the intervention. This study will focus on both the pilot efficacy and process of change examination of a highly personalised intervention, collecting baseline, weekly, post-intervention and follow-up data.

Our research questions are:

(a) Is a highly personalised intervention with weekly feedback provision effective in lowering headache disability and improving headache interference?

(b) Does a personalised intervention lead to changes in clinically targeted psychological processes, personalised goals and headache activity (outcomes)?

Plan of investigation

Design

This is a single-case experimental design (SCED) study, with concurrent multiple baselines within-subjects. We will use an AB design, where baseline (A) will always precede the intervention (B) phase for each participant. This design allows participants to act as their own control (Krasny-Pacini & Evans, 2018), whilst also maintaining experimental control. We will follow the SCRIBE statement (Tate et al., 2016) to guide the reporting of this SCED design.

Each participant will partake in a baseline data collection, between 1 to 2 weeks before we deliver the intervention. Participants will not be able to begin any psychological intervention for headaches during the study. Below, we present all the phases of the study.

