management. Clinical supervision during this treatment phase will be provided by the lead project supervisor who holds extensive clinical and research experience in chronic headaches. Due to the intervention being highly personalised, adherence to a specific treatment protocol will not be measured. Additionally, we will administer a Client Feedback Form at the final session.

Participants will begin interventions at different time points, in line with the Multiple-Baseline SCED Design. This will mean that some participants will spend longer completing Baseline data before they begin the intervention phase. We expect the baseline period to be no longer than 2 weeks at most, ranging from several days to 2 weeks. The multiple baseline design protects validity of research by controlling for the effect of passage of time on the results (Slocum et al., 2022). We aim to randomise participants into multiple baselines, rather than selecting participants, to reduce the risk of researcher bias (Levin and Ferron, 2021).

The data collection schedule will remain the same as in Phase 3 (i.e. on 3 days per week, participants will receive 2-3 prompts to fill out a brief questionnaire, and once per week they will receive a prompt to complete a measure of headache-related disability and interference).

The personalisation will be an ongoing collaborative process. This means that the research team will revise the collected data each week, which will consequently inform each session's focus. Within PBT, the network map is viewed as always changing and therefore is revisited frequently during therapy (Ong et al. 2022). Within our study, we will use the network map as the preliminary case conceptualisation to identify key processes that might be contributing to headache-related disability. Consequently, we will collect weekly EMA data in between intervention sessions, and share this with participants to update the network diagram and to identify the key focus of the subsequent treatment sessions. The PBT network map, along with weekly intensive EMA data collection, during treatment and at follow-up, will help us to create a highly personalised, dynamic psychological intervention. The weekly EMA idiographic data will be reviewed with adolescents and will guide:

- a) Network case formulation
- a) Processes to focus on the personalised intervention
- b) Decision-making on the overall course of treatment.

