1. Perceived progress in a personally defined goal (1 item)
2. Perceived progress in ability to cope with headache (1 item)
3. Headache activity (frequency, duration, intensity and interference) (4 items)

Secondary outcome measures

Participants will respond once per week in a series of standardised measures, using a total of 2 questionnaires as outlined below.

1. Headache interference. The Patient Reported Outcomes Measurement Information System (PROMIS) Paediatric Pain Interference (PPI) Item Bank- 10 items (Varni et al. 2010) measures the daily interference of pain on physical, psychological, and social functioning. Higher scores indicate greater pain interference in the child's life. This is a unidimensional item bank (Varni et al., 2010), derived from a larger PROMIS item bank which has an overall good internal consistency (Cronbach's alpha= 0.98) (Cunningham et al. 2017) and convergent validity shown by significant correlations with other similar scales. The PPI scale has been validated in paediatric chronic pain samples (Ceniza-Bordallo et al., 2022).

2. Measure of headache-related disability. Headache-related disability will be measured using the Paediatric Migraine Disability Assessment Scale (PedMIDAS) (Hershey et al. 2001), which is a 6-item

questionnaire measuring the frequency of disruption to daily activities caused by headaches. This measure has been used in studies measuring headache related disability after pharmacological interventions (Powers et al., 2021). The PedMIDAS has been shown to have internal consistency (Cronbach's alpha 0.80) and validity in measuring headache-related disability (Hershey et al. 2001).

Other measures

Additionally, we will administer a Client Feedback Form at the final intervention session, based on Sekhon et al.'s (2018) theoretical framework of acceptability (TFA) for health interventions. This includes six items, rated on a 5-point Likert scale: affective attitude, burden, perceived effectiveness, intervention coherence, self-efficacy, and opportunity/ costs.

Statistical analyses

To address the first research question, we will analyse the weekly standardised data to assess change in disability (PedMIDAS) and headache interference (PROMIS) assessing reliable change (RC) and clinically significant change (CSC), using Jacobsen & Traux's formula (1991). (Scores will be compared against a calculated reliable change index, to indicate whether the level of change is statistically significant).

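### Headache medication is recorded only once, before baseline, so a change around the start of the intervention could be mistaken for an effect, or hide one, in that participant's A/B comparison

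*Protocol*

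**What the plan says.** Under Demographics and clinical characteristics, the Protocol lists "headache profile (e.g., frequency, intensity, severity), and medication use" among the items to be collected. The timing is fixed: "Demographic information will be collected using Qualtrics between Phase 1 and 2". That is before baseline (Phase 3) and the intervention (Phase 4).

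The repeated measures are listed in full. In Phase 3 participants complete "primary outcome measures (headache activity, progress towards the personalised goal, and coping with headache), and their personalised PBAT items", and Phase 4 keeps the same schedule. The weekly standardised measures are given as "using a total of 2 questionnaires as outlined below", namely PROMIS pain interference and PedMIDAS. Phase 5 continues the daily and weekly measures. None of these is described as recording medication.

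On co-treatment, the Design section says: "Participants will not be able to begin any psychological intervention for headaches during the study". Table 1 excludes recent or current psychological support but sets no criterion on stable medication.

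On control, the Design section says of the AB design: "This design allows participants to act as their own control". Under Phase 4 it adds: "The multiple baseline design protects validity of research by controlling for the effect of passage of time on the results".

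**The concern.** In an AB design without reversal, a participant's phase B is judged against that same participant's phase A. Anything else that changes near the switch and moves headache is a rival explanation for that case. The Protocol recognises this for psychological treatment and bars it, but it neither limits nor tracks headache medication.

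Participants come from a specialist paediatric NHS service. Taking a baseline of 1 to 2 weeks, up to 5 weekly sessions and follow-up of 1 to 2 weeks, each is followed for about 1 + 5 + 1 = 7 to 2 + 5 + 2 = 9 weeks after the form is completed. A medication change in that time is plausible.

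What is at stake is how single cases are interpreted. If the date of a change is never collected, no later analysis plan can mark it, adjust for it or set the case aside.

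**Working it through.** **No stated figure to reproduce.** The Protocol gives no power, alpha or effect size, and sample size rests on precedent. The check has two parts: a reading of what is collected, and an illustration of how large the distortion could be.

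**1. Is medication captured anywhere during phases A, B or follow-up?**
- Demographic form: yes, once, before Phase 2.
- Intake form (Phase 2): described as "The form will assess headache history and coping responses". The form itself is not reproduced, but it is used before phase A in any case.
- Momentary items (Phases 3 to 5): headache activity, goal progress, coping and personalised PBAT items. No medication item is listed.
- Weekly questionnaires: two, neither described as recording medication.
- Regression predictors (Statistical analyses): lagged outcome and PBAT items only.

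As written, the plan can neither detect nor date a medication change after the start of baseline.

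**2. How large could the distortion be in one series?**

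Inputs from the Protocol: phase A of 1 or 2 weeks; phase B of up to 5 weeks; 3 days a week; 2 prompts a day (the lower end of 2 to 3). This gives 1 × 3 × 2 = 6 or 2 × 3 × 2 = 12 points in A, and 5 × 3 × 2 = 30 in B.

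Assumptions, not from the documents: zero therapy effect; a lasting step improvement of 0.5 or 1.0 SD from medication; normal scores; autocorrelation 0 or 0.3. Lower scores mean less headache, so a negative Tau is an apparent improvement.

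Without autocorrelation, the expected A-versus-B Tau is

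Tau = -(2Φ(δ/√2) - 1) × f,

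where δ is the step in SD units and f is the share of A-B pairs that straddle the change. For δ = 1: 2 × 0.760 - 1 = 0.52. For δ = 0.5: 2 × 0.638 - 1 = 0.28.

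| Timing of change | f | Tau, δ = 1 | Tau, δ = 0.5 |
|---|---|---|---|
| Middle of A | 1/2 | -0.26 | -0.14 |
| A/B switch | 1 | -0.52 | -0.28 |
| Start of B week 2 | 24/30 = 0.8 | -0.42 | -0.22 |
| Middle of B | 15/30 = 0.5 | -0.26 | -0.14 |
| Start of B week 5 | 6/30 = 0.2 | -0.10 | -0.06 |

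A simulation of 2,000 series per setting, across both baseline lengths and both autocorrelations, agrees with these means to within about 0.01. The share of series with a nominally significant improvement (z below -1.96) was:

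| Timing of change | δ = 1 | δ = 0.5 |
|---|---|---|
| No change | 2-8% | 2-8% |
| Middle of A | 14-30% | 7-17% |
| A/B switch | 55-78% | 17-35% |
| Start of B week 2 | 33-59% | 13-25% |
| Middle of B | 14-30% | 7-18% |
| Start of B week 5 | 5-13% | 4-10% |

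The no-change row has no step, so its two columns are the same result. With correction for baseline trend, the mid-A figure for a 1 SD step shrinks only to between -0.20 and -0.23.

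**3. What this does not cover.** The simulation concerns Tau and Tau-U only. For reliable change the argument is logical: a medication shift falling between the two scores compared becomes part of their difference. The lagged regression was not simulated.

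**The case against.** **This is an omission, not an error.** The demographic list is an ordinary baseline list, and the Protocol never claims that medication is stable. Flagging and sensitivity analyses are commonly left to the SAP. This stands for the analysis details. It does not stand for data collection: the Protocol fixes what is measured, and an SAP cannot recover dates that were not collected.

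**A reader might infer that every analysis would misread the change as therapy.** The Protocol does not support that. The dynamic regression relates PBAT items to lagged outcomes and does not contrast A with B. A medication step could disturb it, but would not appear there as a therapy effect. Two of the three primary domains are perceived goal progress and perceived coping, and nothing in the documents shows how far medication moves them. A worsening would hide benefit rather than imitate it.

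**A reader might infer that staggered starts give no protection.** That is too strong. In a concurrent multiple-baseline design, the case for an effect is change appearing at each participant's own start. One participant's medication change is unlikely to reproduce that across cases. This protects the overall pattern in part. It does not clear the individual result, and only about 6 completers are expected.

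**A reader might attach a probability.** For example, an assumed 10% chance of change per participant gives 1 - 0.9^6 = 47% for at least one of six. That is the chance of any change in Phases 3 to 5, including late, follow-up and worsening changes, and not of a misleading result. Nor can one case be said to move a responder rate by 1/6, about 17 points: the Protocol defines no such endpoint, and a change need not flip a classification.

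**The therapist may hear of a change.** There are up to five one-to-one sessions with weekly data review, so a date could be learned. The Protocol does not provide for recording it.

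**Conclusion.** The point holds as a gap in data collection, limited mainly to single-case A/B comparisons on headache outcomes. A medication change in late phase A, at the switch or early in phase B could be mistaken for an intervention effect, or could mask one, in that participant's visual analysis, Tau-U and reliable-change result.

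The size depends on timing, direction and strength. Under the illustration's assumptions, a 1 SD improvement gives an apparent Tau from about -0.52 at the switch to about -0.10 at the start of week 5 of phase B, with no therapy effect at all. A 0.5 SD step gives about half of that. These step sizes are assumptions. The documents do not say how often medication changes, so neither the number of affected cases nor the probability of a wrong conclusion can be given. The finding does not show that the study's overall conclusion would be wrong.

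**What to change.** Add one item to the weekly questionnaire throughout Phases 3 to 5: whether any headache medicine was started, stopped or changed that week, and on what date. Days of as-needed use could be added as an option.

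Then:
- mark each change on that participant's graph;
- report affected series separately, and show the summary of cases with and without them;
- repeat Tau-U on pre-change data only where enough phase B data precede the change.

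The last step needs that limit. With 30 points in phase B, the number left before the change is 0 if it falls in A or at the switch, 6 at the start of B week 2, 15 at mid-B and 24 at the start of B week 5. The reanalysis is impossible or weak where the distortion is largest. In those cases the marked graph and the separate report are what help the reader.

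The cost is a few seconds of weekly burden and one small sensitivity analysis. The item should be in place before data collection starts, because later recall may not restore dates reliably. It implies no restriction on treatment.
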